## Aim

In patients with hepatic lesions, to evaluate the efficacy of contrast enhanced ultrasound (CEUS) compared to MRI in differentiating focal nodular hyperplasia (FNH) and hepatic adenoma. Studies from Europe (Dietrich et al, Roche et al) have described different patterns of enhancement between FNH and hepatic adenoma. MRI is the current imaging modality of choice for making this determination, but has limitations. This pilot study aims to test the hypothesis that CEUS has similar ability to differentiate FNH and adenoma, using MRI as the gold standard.

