## Rationale

Hepatic imaging plays an important role in identifying and differentiating both benign and malignant neoplasms of the liver. One of the clinical and radiologic dilemmas facing hepatic medicine is the accurate differentiation of focal nodular hyperplasia (FNH) and hepatic adenoma (HA). This is a question of some import, as there are significant prognosis and treatment differences between these entities, as well as overlap in the patient populations in whom they occur.

FNH is the second most common benign neoplasm of the liver, with a strong female predilection. These lesions are usually asymptomatic and incidentally discovered, and carry only a small risk of complication such as bleeding. There is no malignant potential. Hepatic adenomas (HAs) are more rare benign neoplasms that also have a female predilection. However, these lesions are more likely to be symptomatic, and carry a higher bleeding risk especially as they grow over 4 cm. In addition, they harbor a small risk of malignant transformation to hepatocellular carcinoma (HCC). Of note, patients may present with both types of lesion concurrently.

Currently, MRI with hepatobiliary contrast agents is the standard for differentiation of these lesions. These agents (such as gadoxetate disodium, or Eovist) are actively transported into hepatocytes, which are present in FNH and only in very rare cases with HA. Previous research (such as from Grazioli et al.) has shown that hepatobiliary agents can differentiate these lesions with excellent accuracy. However, there is still overlap between these lesions on imaging, and for certain patients MRI may be difficult or impossible.

FDA approval of contrast enhanced ultrasound (CEUS) agents in 2016 has opened a new avenue for abdominal imaging. CEUS utilizes gas containing lipid microbubbles to provide pure intravascular contrast, allowing for evaluation of vascular and solid organ perfusion. It has an excellent safety profile and is not excreted by the kidneys, allowing for use in patients with acute and chronic renal disease. It has been used for some time outside of the US for liver lesion evaluation, and the enhancement patterns of both FNH and HA have been described in the literature as having different appearances. CEUS can be especially useful for focal liver lesion

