imaging for patients who cannot or will not undergo MRI, and it has the advantages of flexibility, increased temporal resolution, and decreased cost. This study aims to compare the utility of CEUS for differentiating FNH and HA with the current standard of hepatobiliary contrast MRI.

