## **Patient selection**

### *Inclusion criteria*

1. Males and females
2. Age 18 years or greater
3. Recently have undergone (within 365 days) or are scheduled to undergo abdominal MRI with contrast at a performance site for evaluation of a hepatic lesion(s).

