The subjects will be scanned in the University or Methodist Hospital ultrasound department by technicians trained in use of CEUS, under supervision of one of the study's key personnel. The contrast agent used will be Lumason (sulfur hexafluoride lipid-type A microspheres) distributed by Bracco Diagnostics Inc. Previous MRI images will be reviewed, and up to two of the largest lesions will be evaluated. Each lesion will be interrogated with a single intravenous dose of contrast (2.5 mL). If there is a single lesion, a second 2.5 mL injection may be used as needed to improve lesion visualization. If there are two lesions, each will be evaluated with one injection. Since the intention to treat includes all lesions chosen from MRI, if the injection(s) do not provide adequate images, the lesion in question will not be excluded from the study.

Once the study is closed to enrollment and all subjects have completed the research CEUS scan. The obtained CEUS images will then be reviewed in consensus by two radiologist investigators, blinded to clinical information and MRI findings. Each lesion assessed will be given a presumed diagnosis of FNH, HA, or indeterminate. At the completion of the study, the CEUS data will be compared to the official reports from the MRIs dictated by IUH radiologists to assess concurrence between the two imaging modalities.

The PI and another investigator will quarterly review data quality, subject recruitment, accrual, outcome and adverse event data; assess scientific reports or therapeutic development, results of related studies that may impact subject safety, and procedures designed to protect the privacy of subjects.

We will compile descriptive statistics comparing the sensitivity, specificity, and accuracy of CEUS for differentiating FNH and hepatic adenoma, compared with MRI results as the gold standard.

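### MRI is both comparator and gold standard, so the planned accuracy figures are agreement with MRI: they bound a difference in accuracy but cannot test similar ability

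*Protocol*

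**What the plan says.** The Aim sets CEUS against MRI and gives MRI a second role in the same sentence: "This pilot study aims to test the hypothesis that CEUS has similar ability to differentiate FNH and adenoma, using MRI as the gold standard". The Rationale repeats MRI as the comparator: "This study aims to compare the utility of CEUS for differentiating FNH and HA with the current standard of hepatobiliary contrast MRI".

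On the quality of MRI the protocol says two things. It reports that "hepatobiliary agents can differentiate these lesions with excellent accuracy", and then continues: "However, there is still overlap between these lesions on imaging, and for certain patients MRI may be difficult or impossible". The Aim also says: "MRI is the current imaging modality of choice for making this determination, but has limitations".

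In Methods, two blinded radiologists read the CEUS images in consensus: "Each lesion assessed will be given a presumed diagnosis of FNH, HA, or indeterminate". These calls are set against the official MRI reports "to assess concurrence between the two imaging modalities". The last paragraph of Methods then plans descriptive sensitivity, specificity and accuracy of CEUS, with the MRI result as truth. Enrollment states that there was no basis for sizing a study of equivalence and sets 40 patients on practical grounds. The protocol text available for this review names no other reference, such as pathology or follow-up.

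**The concern.** A claim of similar ability needs an estimate of ability for each of two tests. When one of them is also the truth, it scores 100% by construction and nothing is learned about it. The other test's accuracy is then percent agreement under another name, and each lesion on which the two give opposite FNH/HA calls is booked as a CEUS error, even though the protocol itself says MRI is not free of overlap.

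The result can mislead in either direction. A CEUS as good as MRI could be reported as less accurate, most visibly for HA, which the Rationale describes as the rarer lesion. A CEUS that repeats MRI's mistakes could be reported as more accurate than it is. The Rationale says that the distinction matters for prognosis and treatment, so a reader will take the words sensitivity and specificity seriously.

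**Working it through.** The protocol has no figure to reproduce here: it gives no alpha, power, margin or accuracy rates. The check is therefore what a CEUS-by-MRI table can and cannot identify.

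**Inputs.** From the protocol: 40 patients, up to two lesions each (at most 80), and CEUS calls of FNH, HA or indeterminate. Assumed, because the documents give no values: the same true accuracy *a* for both tests (98%, 95%, 90%), an FNH share *p* of 80%, and a correlation *r* between the two tests' errors of 0 or 0.5.

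**1. One table, several truths.** Suppose CEUS and MRI agree on 36 of 40 lesions, the four others are opposite FNH/HA calls, and the agreed calls are right. The same table arises if
- MRI is perfect and CEUS is 36/40 = 90% accurate (difference −10 points);
- CEUS is perfect and MRI is 90% accurate (+10 points);
- each is wrong on two of the four (0 points).

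The planned labels report only the first.

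**2. What agreement does give.** Let *b* be the share of lesions where only CEUS is right and *c* the share where only MRI is right. Then accuracy(CEUS) − accuracy(MRI) = *b* − *c*, and |*b* − *c*| ≤ *b* + *c* ≤ *D*, the share of lesions on which the calls differ. This holds with indeterminate calls too. The size of the difference is bounded; its sign is not known.

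**3. The bound with sampling error** (exact two-sided 95% upper limit of *D*, lesions treated as independent):

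| Discordant | Upper limit |
|---|---|
| 0/40 | 8.8 points |
| 2/40 | 16.9 points |
| 4/40 | 23.7 points |
| 0/80 | 4.5 points |
| 4/80 | 12.3 points |

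The 80-lesion rows are optimistic, because two lesions in one patient are correlated.

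**4. Indeterminate CEUS calls.** If a lesion truly is FNH or HA, an indeterminate call cannot be a correct diagnosis. If all four discordances in 40 are of this kind, *b* = 0 and the difference lies between −10 and 0 points. For these lesions the direction is partly known.

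**5. Size of the distortion.** With *e* = 1 − *a*, both right is R = *a*² + *r·a·e* and both wrong is W = *e*² + *r·a·e*.
- Overall agreement = R + W = 1 − 2*ae*(1 − *r*). For *a* = 0.98, *r* = 0: 1 − 2 × 0.98 × 0.02 = 0.961.
- Agreement among lesions MRI calls HA = [*p*W + (1 − *p*)R] / [*pe* + (1 − *p*)*a*]. For *a* = 0.98, *r* = 0: (0.8 × 0.0004 + 0.2 × 0.9604) / (0.016 + 0.196) = 0.1924/0.212 = 0.908.

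| True accuracy of both | Overall, r = 0 | Overall, r = 0.5 | MRI-HA, r = 0 | MRI-HA, r = 0.5 |
|---|---|---|---|---|
| 98% | 96.1% | 98.0% | 90.8% | 95.4% |
| 95% | 90.5% | 95.3% | 79.3% | 89.7% |
| 90% | 82.0% | 91.0% | 65.4% | 82.7% |

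Overall agreement equals true accuracy when *r* = 1 − 1/(2*a*), that is 0.490, 0.474 and 0.444. Below that value CEUS is understated; above it, overstated. With independent errors and an FNH share from 50% to 90%, the MRI-HA figure at 98% accuracy runs from 96.1% down to 83.1%.

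**The case against.** The strongest reply is that nothing is hidden. The protocol names MRI as the gold standard, describes the comparison as concurrence, calls the study a pilot, plans descriptive statistics only, and admits that it is not sized for equivalence. Accuracy against a named reference is conventional, and MRI is a reasonable reference if its accuracy is as good as the Rationale says. At 98% the overall distortion is about 2 points, less than sampling error: 38/40 agreement has an exact 95% interval of 83.1% to 99.4%. The large HA figures need lower MRI accuracy, independent errors and a high FNH share, none of which the documents give. All of this stands, and it lowers the severity. It does not make the hypothesis in the Aim testable, because MRI's accuracy is still never estimated.

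Some stronger readings are tempting but not supported.
- A reader might infer that no disagreement should count against CEUS. That is wrong for indeterminate CEUS calls (step 4); a blanket rule would hide real failures to diagnose.
- A reader might infer that agreement says nothing about similarity. It does bound the overall difference (step 2).
- A reader might turn the overall bound into one for HA by dividing by the HA share. The protocol gives no such share, and the true share cannot be identified from these data, so such a figure would rest on an assumption alone.
- A reader might infer that the direction can never be known. With binary calls, an outside figure for MRI accuracy would settle it if disagreement exceeded 2 × (1 − MRI accuracy), for example 10% at an accuracy of 95%. The protocol supplies no such figure.

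**Conclusion.** The point holds and should be fixed; it is not a fatal flaw. As written, the planned sensitivity, specificity and accuracy measure agreement with the MRI report. For opposite FNH/HA calls they cannot show which test erred or which is more accurate, so similar ability cannot be tested. What can be said is a bound on the size of the difference, and only among lesions MRI reports as FNH or HA: 8.8 points at best with 40 single lesions, 23.7 points with four discordant.

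The distortion from treating MRI as truth is modest overall if MRI is near 98% accurate: about 2 points with independent errors, about 0 at error correlation 0.5. For HA it is about 7 points at an assumed 80% FNH share, falling to under 3 at correlation 0.5. Every one of these inputs is an assumption. The identification argument and the bound need none of them; the numerical limits need only independent lesions.

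A statistical analysis plan could add intervals, but it could not produce MRI's accuracy without another reference.

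**What to change.** **Aim.** Replace the hypothesis sentence with: *estimate the agreement between CEUS and MRI in classifying lesions as FNH or HA.*

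**Methods, last paragraph.** Report as agreement with MRI:
- the share of MRI-FNH lesions that CEUS calls FNH;
- the share of MRI-HA lesions that CEUS calls HA;
- overall agreement.

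Keep indeterminate CEUS calls in the denominator as non-agreement, show them separately, and read them as CEUS failures to diagnose. State that opposite FNH/HA calls will not be read as CEUS errors. Limit any similarity statement to: *among lesions MRI reports as FNH or HA, overall accuracies differ by no more than X*, with X the upper confidence limit of the discordance rate.

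**Cost.** Wording in two places. Enrollment, blinding and imaging do not change. The price is a weaker claim, with a wide bound at 40 patients.

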## Rationale

Hepatic imaging plays an important role in identifying and differentiating both benign and malignant neoplasms of the liver. One of the clinical and radiologic dilemmas facing hepatic medicine is the accurate differentiation of focal nodular hyperplasia (FNH) and hepatic adenoma (HA). This is a question of some import, as there are significant prognosis and treatment differences between these entities, as well as overlap in the patient populations in whom they occur.

FNH is the second most common benign neoplasm of the liver, with a strong female predilection. These lesions are usually asymptomatic and incidentally discovered, and carry only a small risk of complication such as bleeding. There is no malignant potential. Hepatic adenomas (HAs) are more rare benign neoplasms that also have a female predilection. However, these lesions are more likely to be symptomatic, and carry a higher bleeding risk especially as they grow over 4 cm. In addition, they harbor a small risk of malignant transformation to hepatocellular carcinoma (HCC). Of note, patients may present with both types of lesion concurrently.

Currently, MRI with hepatobiliary contrast agents is the standard for differentiation of these lesions. These agents (such as gadoxetate disodium, or Eovist) are actively transported into hepatocytes, which are present in FNH and only in very rare cases with HA. Previous research (such as from Grazioli et al.) has shown that hepatobiliary agents can differentiate these lesions with excellent accuracy. However, there is still overlap between these lesions on imaging, and for certain patients MRI may be difficult or impossible.

FDA approval of contrast enhanced ultrasound (CEUS) agents in 2016 has opened a new avenue for abdominal imaging. CEUS utilizes gas containing lipid microbubbles to provide pure intravascular contrast, allowing for evaluation of vascular and solid organ perfusion. It has an excellent safety profile and is not excreted by the kidneys, allowing for use in patients with acute and chronic renal disease. It has been used for some time outside of the US for liver lesion evaluation, and the enhancement patterns of both FNH and HA have been described in the literature as having different appearances. CEUS can be especially useful for focal liver lesion

imaging for patients who cannot or will not undergo MRI, and it has the advantages of flexibility, increased temporal resolution, and decreased cost. This study aims to compare the utility of CEUS for differentiating FNH and HA with the current standard of hepatobiliary contrast MRI.

## **Patient selection**

### *Inclusion criteria*

1. Males and females
2. Age 18 years or greater
3. Recently have undergone (within 365 days) or are scheduled to undergo abdominal MRI with contrast at a performance site for evaluation of a hepatic lesion(s).

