## **Methods**

Potential subjects will be identified by three methods.

- 1) From the MRI schedule at the performance site, a radiology investigator will prospectively identify patients who are to undergo abdominal MRI with hepatobiliary contrast and who otherwise meet entry criteria. Exclusion criteria will be evaluated by consulting the medical record. At the time of MRI scanning, a radiology investigator will meet with the potential subject, confirm that exclusion criteria are not met, explain the study, answer any questions, and seek written informed consent. If consent is granted, CEUS of the liver will be scheduled.
- 2) From the surgery/hepatology clinic schedule, a surgery or hepatology investigator will identify patients who meet entry criteria. The investigator will explain the study to the patient; if he/she expresses interest, the investigator will give a copy of the informed consent to the potential subject, and contact radiology and have the patient scheduled for CEUS of the liver. At the time of CEUS, a radiology investigator will meet with the potential subject, confirm that exclusion criteria are not met, explain the study, answer any questions, and seek written informed consent.
- 3) The principle investigator will retroactively review the radiology database, DORIS, for patients who have had a recent MRI with hepatobiliary contrast and who otherwise meet entry criteria that may have been missed by the previous methods mentioned. A study

radiology investigator will reach out to the patient's hepatologist about enrolling them in the trial and obtain best contact information. A study coordinator will contact the patient by email or phone, with IRB approved script, to seek consent to contact for recruitment purposes.

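### Inclusion criterion 3 does not name hepatobiliary contrast, so patients recruited from clinic can bring a different MRI reference standard

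*Protocol*

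**What the plan says.** **Comparator.** The Rationale states: "Currently, MRI with hepatobiliary contrast agents is the standard for differentiation of these lesions". It explains this by uptake of these agents into hepatocytes, and cites earlier work as showing that "hepatobiliary agents can differentiate these lesions with excellent accuracy". It closes by setting CEUS for FNH versus HA against that modality: "with the current standard of hepatobiliary contrast MRI".

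**Eligibility.** Inclusion criterion 3 requires a recent or scheduled "abdominal MRI with contrast at a performance site for evaluation of a hepatic lesion(s". It names no class of agent. The three exclusion criteria (cardiac ischemia, hypersensitivity to the ultrasound agent, pregnancy) do not touch on the MRI agent.

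**Recruitment (Methods).**
- Route 1, the MRI schedule: "patients who are to undergo abdominal MRI with hepatobiliary contrast and who otherwise meet entry criteria".
- Route 2, the clinic schedule: "a surgery or hepatology investigator will identify patients who meet entry criteria".
- Route 3, the radiology database: "patients who have had a recent MRI with hepatobiliary contrast and who otherwise meet entry criteria".

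**Reference and outcomes (Methods).** The CEUS diagnosis (FNH, HA or indeterminate) is compared with the official clinical MRI report. Sensitivity, specificity and accuracy are then described with MRI as the gold standard.

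**The concern.** The case for MRI as gold standard is made for one class of agent. Two of the three recruitment routes carry that restriction in their own wording. The third passes the question to the entry criteria, which do not contain it. The reference standard could therefore be hepatobiliary MRI for some patients and MRI with another agent for others, and nothing in the protocol would mark this as a deviation.

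At stake is the meaning of the only stated results. Sensitivity, specificity and accuracy are read against the MRI report. If some reports come from an examination to which the protocol's accuracy argument does not apply, disagreement with CEUS in those patients cannot be interpreted in the same way. The agent cannot be changed afterwards: criterion 3 accepts an MRI done up to 365 days earlier, so for some patients it is fixed before they are approached.

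**Working it through.** The protocol gives no figure to reproduce here. Its 40 patients reflect availability, and it disclaims a power calculation. The main check is textual.

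**Step 1. The places side by side**

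| Place | MRI agent required |
|---|---|
| Aim | MRI, agent not stated |
| Rationale, closing sentence | Hepatobiliary |
| Inclusion criterion 3 | Any contrast |
| Exclusion criteria | Silent |
| Methods, route 1 | Hepatobiliary |
| Methods, route 2 | Whatever the entry criteria require |
| Methods, route 3 | Hepatobiliary |
| Methods, lesion selection and reading | MRI, agent not stated |

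**Step 2. A route 2 patient followed through the text.** A clinic patient had a contrast MRI with a non-hepatobiliary agent at a performance site within the last year. Criterion 3 is met and no exclusion applies. Route 2 adds no condition, and at the CEUS visit the radiology investigator is asked only to confirm that exclusion criteria are not met. The official report of that MRI is then the reference. The same patient would not be picked up by route 1 or route 3. The gap is real and lies in route 2 only.

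**Step 3. How many patients.** The protocol does not say how many will come by each route or which agents clinic patients receive. With no cap, the text allows 0 to 40, each patient being 1/40 = 2.5%. Let r be the share recruited by route 2 and s the share of those with another agent, both assumed. The number affected is 40 × r × s:
- r = 10%, s = 10%: 40 × 0.10 × 0.10 = 0.4 patients (1%)
- r = 33%, s = 25%: 40 × 0.33 × 0.25 = 3.3 patients (8.25%)
- r = 50%, s = 50%: 40 × 0.50 × 0.50 = 10 patients (25%)

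**Step 4. What that could do to agreement (illustration only).** Assume that CEUS is right in a = 90% of lesions, that hepatobiliary MRI is right in 95%, that MRI with another agent is right in e = 70% to 90%, that the read has two classes with independent errors, and that a share m of lesions has the other reference. None of these values is in the protocol. Then

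R = (1 − m) × 0.95 + m × e, and apparent agreement A = a × R + (1 − a) × (1 − R).

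- m = 0: R = 0.95, A = 0.90 × 0.95 + 0.10 × 0.05 = 86.0%
- m = 1%: R = 0.9475 to 0.9495, A = 85.8% to 86.0%
- m = 25%: R = 0.8875 to 0.9375, A = 81.0% to 85.0%

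Under these assumptions apparent agreement falls by at most 0.2 points at the low end and by 1 to 5 points at the high end. For scale, the exact 95% interval for 36 of 40 correct (90.0%) runs from 76.3% to 97.2%, a width of 20.9 points.

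**The case against.** The strongest reply is that this is loose drafting. Routes 1 and 3 ask for hepatobiliary MRI in patients who *otherwise* satisfy the entry criteria, which treats the agent as one of those criteria. Route 3 is described as catching patients whom the other two methods missed, which implies that all three draw on the same pool. The Rationale calls hepatobiliary MRI the standard for these lesions, so most clinic patients may have had it anyway. The Aim and the outcome sentence say only MRI, so criterion 3 agrees with them; its conflict is with the Rationale and with routes 1 and 3. The study is also a descriptive pilot with no formal test to distort.

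All of this stands as evidence of intent and as a limit on size. It does not close the gap: an investigator who follows route 2 and criterion 3 to the letter may enroll a patient whose MRI used another agent.

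Stronger readings are tempting but are not supported.
- *The population is too broad.* A reader might infer that admitting any hepatic lesion is an error. The Aim itself opens "In patients with hepatic lesions", so criterion 3 agrees with it.
- *Lesions that MRI reports as another entity must be kept and will spoil the analysis.* The intention-to-treat remark in Methods is the premise of one rule, that a lesion is not dropped for inadequate CEUS images. It does not address other diagnoses, and how these count may properly be left to the SAP.
- *Lesions should be chosen by their MRI diagnosis.* That would make selection depend on the reference standard. Choosing by size does not.
- *A known share of the reference is mixed.* No passage gives any frequency.

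**Conclusion.** The mismatch is confirmed on the text. The Rationale and routes 1 and 3 specify hepatobiliary MRI; criterion 3 does not, and route 2 has no condition of its own. The reference standard can therefore come from a different class of agent, through route 2 only.

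The extent is unknown. The text bounds it at 0 to 40 patients, and the assumed shares give 0.4 to 10. The effect on apparent agreement, from negligible to about 5 points, rests wholly on assumed accuracies and independent errors, and should not be quoted as an estimate. The wording should be corrected because part of the effect cannot be undone once patients are enrolled, and the correction is small. It does not invalidate the design.

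A lesser point remains about the read. Lesions are taken by size alone and the MRI report may name any entity, while the CEUS reader has only FNH, HA or indeterminate. A lesion that the reader recognizes as something else would share a label with one that cannot be classified. This is optional to address.

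**What to change.** **Main change.** In inclusion criterion 3, insert the word hepatobiliary before contrast, so that the condition binds all three routes. Leave the hepatic-lesion population as it is. If the sponsor did mean to accept other agents, the Rationale and routes 1 and 3 would have to be reconciled with that instead, but their present wording points the other way.

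**Cost.** One word. Some clinic patients whose MRI used another agent become ineligible, so accrual may slow slightly.

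**Optional.** Add *other* to the CEUS diagnosis labels. Methods places the blinded read after enrollment closes and all scans are complete, so the read form can be changed until then at the cost of one extra option. Keep the size-based lesion selection, and leave the counting of *other* lesions in the accuracy measures to the SAP.
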